9.3.2.4 Site(s) Performing Correlative Study: [REDACTED] laboratory, Mayo Clinic

9.3.3 **Assay for Topo I-DNA covalent complexes – Exploratory/Ancillary Laboratory Correlative Study #3**

9.3.3.1 Collection of Specimen(s): Patients will have at least 5 ml samples of peripheral blood collected in a 6 ml tube containing EDTA as an anticoagulant (lavender top) at the time points specified below.

- 1: PRE-TREATMENT/SCREENING (preferably at the same time as on-study marrow)
- 2: Immediately before start of topotecan/carboplatin infusion
- 3: 48-96 hours into the 5-day topotecan/carboplatin infusion

9.3.3.2 Handling of Specimens(s): No processing needed. Samples will be shipped to [name] laboratory at Mayo Clinic for assay of topo I-DNA covalent complexes.

9.3.3.3 Shipping of Specimen(s): Peripheral blood specimens will be shipped on the day they are drawn to Dr. [REDACTED], Mayo Clinic, overnight by Federal Express. Ship purple top tubes (5 cc peripheral blood) harvested prior to therapy, prior to initiation of topotecan/carboplatin infusion and once 48-96 hours into the topotecan/carboplatin infusion to

[REDACTED], M.D., Ph.D.  
Division of Oncology Research  
[name]  
Mayo Clinic  
[name]  
[name]

During the spring, summer and autumn these samples should be packed in styrofoam containers containing cold packs (but shielded from freezing). During the winter ice packs should be omitted but styrofoam shipping containers should still be used to prevent the freezing of samples en route.

These samples should be shipped Monday-Thursday. At the time samples are shipped, please e-mail Dr. [REDACTED] and copy [REDACTED] with the FedEx tracking number to facilitate sample accessioning and analysis.

9.3.3.4 Site(s) Performing Correlative Study: [REDACTED] laboratory, Mayo Clinic

**9.3.4 Whole Exome Sequencing – Exploratory/Ancillary Laboratory Correlative Study #4.**

9.3.4.1 Collection and Handling of Specimen(s): Gene mutation analysis via whole exome sequencing will be performed at the NCI per attached substudy methods and techniques. Whole exome sequencing will be performed on pre-treatment samples containing 100 ng of DNA previously collected and stored as allowed by protocol. Germline DNA will be obtained thru isolation of T-cells from pre-treatment peripheral blood sampling sent to JHH MDL prior to therapy.

Patients will have 3 ml of peripheral blood collected in a 3 ml lavender EDTA tube. No processing needed. Refrigerate and ship overnight via Federal Express with cold pack. Do not freeze.

9.3.4.2 **Shipping of Specimen(s):** Ship one lavender top tube (3ml peripheral blood) harvested prior to therapy and the Shipping Manifest form, available on the CTSU website, by Federal Express overnight with cold pack to (no receipt on Saturday, Sunday or holidays):

Molecular Diagnostics Lab  
Johns Hopkins Genomics  
[name]  
[name]

Notify the Molecular Diagnostics Lab of the upcoming shipment, preferably 24 hours prior to sending the specimens: [[contact]](mailto:[contact]).

Specimens with an expected delivery day of Saturday, Sunday or holiday may be held refrigerated at 4 degrees C until shipped.

Harvested DNA specimens will be shipped from SKCCC MDL to the MoCha lab.

9.3.4.3 **Site(s) Performing Correlative Study:** DNA libraries for WES will be generated at the central sequencing laboratories by standard procedures. Sequencing will be carried out on an Illumina HiSeq 2500 sequencer and these results will have variant calling through the procedures associated with the Genomic Data Commons. Analysis of sequencing results will be performed at Johns Hopkins. Mutation status will be correlated with clinical outcomes for the patients on study.

#### **9.3.5 Analysis of 5-mC and 5-h-mC – Exploratory/Ancillary Laboratory Correlative Study #5.**

9.3.5.1 **Collection and Handling of Specimen(s):** Analysis of 5-methylcytosine (5-mC) and 5-hydroxymethylcytosine (5-h-mC) will be performed in the laboratory of [REDACTED] at Mayo Clinic. 5-mC will be analyzed RRBS and a 850 kb array; and 5-h-mC will be analyzed by DIP-seq, TAB-RRBS, and 5-H-MC pull down. These analyses will be performed on pre-treatment samples containing 500 ng of DNA previously collected and stored as allowed by protocol. Patients will have 5 ml of peripheral blood collected in a lavender EDTA tube.

Patients will have at least 5 ml of peripheral blood collected in a 6 ml lavender EDTA tube.

9.3.5.2 **Shipping of Specimen(s):** Peripheral blood specimens will be shipped on the day they are drawn to Dr. [REDACTED], Mayo Clinic, overnight by Federal Express. Ship purple top tube (5 cc peripheral blood) harvested prior to therapy to:

[REDACTED], M.D., Ph.D.  
Division of Oncology Research  
[name]  
Mayo Clinic  
[name]

[name]

During the spring, summer and autumn these samples should be packed in styrofoam containers containing cold packs (but shielded from freezing). During the winter ice packs should be omitted but styrofoam shipping containers should still be used to prevent the freezing of samples en route.

These samples should be shipped Monday-Thursday. At the time samples are shipped, please e-mail Dr. [REDACTED] and copy [REDACTED]  
[REDACTED] with the FedEx tracking number to facilitate sample accessioning and analysis.

9.3.5.3 Site(s) Performing Correlative Study: [REDACTED] laboratory, Mayo Clinic

**9.3.6 Samples of viably frozen cells for ChIPseq – Exploratory/Ancillary Laboratory Correlative Study #6.**

9.3.6.1 Collection and Handling of Specimen(s): Analysis of selected chromatin modifications by ChIPseq (chromatin immunoprecipitation followed by sequencing). These analyses will be performed on viably frozen cells after thawing.

Patients will have 7 ml of peripheral blood collected in a 10 ml lavender EDTA tube.

9.3.6.2 Shipping of Specimen(s): Peripheral blood specimens will be shipped on the day they are drawn to Dr. [REDACTED], Mayo Clinic, overnight by Federal Express. Ship purple top tube (7 cc peripheral blood) harvested prior to therapy to

[REDACTED], M.D., Ph.D.  
Division of Oncology Research  
[name]  
Mayo Clinic  
[name]  
[name]

During the spring, summer and autumn these samples should be packed in styrofoam containers containing cold packs (but shielded from freezing). During the winter ice packs should be omitted but styrofoam shipping containers should still be used to prevent the freezing of samples en route.

These samples should be shipped Monday-Thursday. At the time samples are shipped, please e-mail Dr. [REDACTED] and copy [REDACTED]  
[REDACTED] with the FedEx tracking number to facilitate sample accessioning and analysis.

9.3.6.2 Site(s) Performing Correlative Study: [REDACTED] laboratory, Mayo Clinic

## 10. STUDY CALENDAR

Baseline evaluations are to be conducted within 1 week prior to start of protocol therapy. Baseline labs must be repeated if done greater than 7 days prior to C1D1. In the event that the patient's condition is deteriorating, laboratory evaluations should be repeated within 48 hours prior to initiation of the next cycle of therapy.

	Pre-Reg	Pre-Rand	Day1-7								Day 8-13	Day 14 (± 2d)	Day 15-22 (+/- 2d)	Recovery assessment (day 28-42)
Veliparib ARM A			A	A	A	A	A	A	A	A	A		A	A
Topotecan/Carboplatin ARM A					A	A	A	A	A					
Topotecan/Carboplatin ARM B			B	B	B	B	B							
Informed consent	X													
Demographics		X												
Medical history		X												
Concurrent meds		X			X-----X									
Physical exam		X	X			X					X			
Vital signs		X	X			X					X			
Height		X												
Weight		X	X	X	X	X	X	X	X	X	X			
Performance status		X	X											X
CBC w/diff, plts		X	X	X	X	X	X	X	X	X	X	X	X	
Serum chemistry a		X	X	X	X	X	X	X	X	X	X	X	X	
ECG (as indicated)		X												
Tumor Lysis Labs d		X	X	X	X	X	X				X	X (day 22)		
Adverse event evaluation					X-----X									X
B-HCG			X b											
Bone marrow Aspirate/Biopsy c	X										X e			X
Peripheral blood sample g		X g			X g		X g							
Leukemia mutation panel /Whole exome sequencing sample		X												
RAD51 Assay		X												
Pharmacokinetic blood f		X								X	X	X		
WES peripheral blood for T cells		X												

		
A: Veliparib 80mg PO BID day 1-21
 
a: Albumin, alkaline phosphatase, total bilirubin, bicarbonate, BUN, calcium, chloride, creatinine, glucose, potassium, total protein, SGOT [AST], SGPT [ALT], sodium.
 
b: Serum pregnancy test (women of childbearing potential).
 
c: Cytogenetics, immunophenotype, histochemistries; bone marrow aspirate and/or biopsy as medically indicated and to document remission. Bone marrow PK(screening)
 
d: Phosphorous, Uric Acid, LDH, PT, APPT, Fibrinogen,
 
e: Day 14 bone marrow assays: Aspirate differential, Bone marrow core, bone marrow PK.
 
f: ARM A only See Section 9. Day 15 PK +/- 2d, Day 22 PK, only day 20 or 21 pre-treatment is allowed alternative
 
g: For patients with greater than 5000 circulating blasts/mcm^3, one peripheral blood sample harvested at the time of on-study marrow, one right before initiation of topotecan/carboplatin infusion, and third after 48-72 hours of topotecan/carboplatin administration will be assayed for detectable topo I-DNA covalent complexes.

--	--	---

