## 5. TREATMENT PLAN

### 5.1 Agent Administration

Treatment will be administered on an inpatient basis. Reported adverse events and potential risks are described in Section 7. Appropriate dose modifications are described in Section 6. No investigational or commercial agents or therapies other than those described below may be administered with the intent to treat the patient's malignancy. Patient's adherence to oral therapy will be documented through hospital charting.

Arm A : Veliparib 80 mg by mouth twice daily days 1-21. Topotecan 1.2 mg/m^2/d and Carboplatin 150 mg/m^2/day continuous intravenous infusion (CIV) over 5 days for a total of 120 continuous hours on days 3-7.

Arm B : Topotecan 1.6 mg/m^2/d and Carboplatin 150 mg/m^2/day continuous intravenous infusion (CIV) over 5 days for a total of 120 continuous hours on days 1-5.

Regimen Description					
Agent	Premedications; Precautions	Dose	Route	Schedule	Cycle Length
Topotecan	Premedicate with minimum of ondansetron 8 mg IV twice daily	ARM A: 1.2 mg/m  /day in 250 mL D5W ARM B: 1.6 mg/m  /day in 250 mL D5W	IV as continuous infusion over 24 hours for 5 days	Days 3-7*** (ARM A) or Days 1-5*** (ARM B)	28 days: if responding, second cycle can be administered as early as day 28 but no later than day 63. Responding patients may receive up to 3 more cycles (4 total) (see Section 6.1 )
Carboplatin		150 mg/m  /day in 250 cc D5W	IV as continuous infusion over 24 hours for 5 days	Days 3-7*** (ARM A) or Days 1-5*** (ARM B)	
Veliparib**		80 mg	PO twice daily	Days 1-21 (ARM A)	

\*\*Randomized administration.  
\*\*\*Begins at the start of Day 3 or 1 and runs for 5 days continuously, i.e., through the end of Day 7 or 5

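### The study calendar's single topo I-DNA blood row fits the infusion timing of Arm A only; in Arm B its Day 3 and Day 5 marks fall 48–72 h and 96–120 h into the infusion

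*Combined protocol and SAP*

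**What the plan says.** Section 9.3.3.1 asks for three blood samples for the topo I-DNA assay. The first is "PRE-TREATMENT/SCREENING (preferably at the same time as on-study marrow". The second is "Immediately before start of topotecan/carboplatin infusion", and the third is "48-96 hours into the 5-day topotecan/carboplatin infusion". The Section 9.1 table gives the third time as 72 ± 24 into the infusion.

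In Section 10 the row "Peripheral blood sample" has one set of marks for both arms. Each mark carries footnote g, which repeats the screening draw and then asks for "one right before initiation of topotecan/carboplatin infusion, and third after 48-72 hours of topotecan/carboplatin administration". The footnote applies this only to patients with more than 5000 circulating blasts, a limit that 9.3.3.1 does not state.

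Section 5.1 fixes the infusion clock. It runs "for a total of 120 continuous hours on days 3-7" in Arm A and "for a total of 120 continuous hours on days 1-5" in Arm B, with the note "Begins at the start of Day 3 or 1 and runs for 5 days continuously".

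Nothing limits this assay to one arm. The veliparib pharmacokinetic samples, by contrast, are labelled as Arm A only in both Section 9 and the calendar.

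**The concern.** The arms start the infusion two days apart, yet the calendar gives both arms the same sampling days. Days that fit one arm cannot fit the other. A coordinator working from the calendar would draw Arm B blood at times that the row's own footnote does not allow, and a missed pre-infusion draw cannot be recovered.

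At stake is secondary objective 4c, topotecan-induced stabilization of topo I-DNA complexes. If samples are later compared by number, samples 2 and 3 mean before and during infusion in Arm A, but mid and late infusion in Arm B. Sections 13.5 and 13.6 describe analyses for the mutation panel and RAD51 but none for this assay, so no stated rule would re-index the samples by infusion hours.

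**Working it through.** **Step 1: which days are marked.** The extracted table does not label the single days of the infusion week, so I counted columns and calibrated them on the two infusion rows of the same table.

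- Arm A infusion: columns 5–9, which Section 5.1 makes Days 3–7.
- Arm B infusion: columns 3–7, which Section 5.1 makes Days 1–5.
- Topo I-DNA blood: columns 2, 5 and 7.

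Both infusion rows give the same mapping (column 3 = Day 1), so the marks are Pre-Rand, Day 3 and Day 5.

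**Step 2: hours into the infusion.** With start day s (3 in Arm A, 1 in Arm B) and the Section 5.1 convention, calendar day d covers 24(d − s) to 24(d − s + 1) hours.

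| Arm | Day | Hours into infusion | In 48–72 h (footnote g) | In 48–96 h (9.3.3.1) |
|---|---|---|---|---|
| A | 3 | 0–24 (draw possible just before 0) | sample 2 day | sample 2 day |
| A | 5 | 48–72 | yes | yes |
| B | 1 | 0–24 (draw possible just before 0) | sample 2 day, **not marked** | sample 2 day, **not marked** |
| B | 3 | 48–72 | yes | yes |
| B | 4 | 72–96 | no, except at 72 h | yes, not marked |
| B | 5 | 96–120 | no | no, except at 96 h |

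The stated timing reproduces for Arm A and not for Arm B. From the text alone, Arm B's sample 2 belongs on Day 1 and its sample 3 on Day 3, or on Days 3–4 under the wider window.

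**Step 3: sensitivity to clock time.** Let δ be the draw's clock time minus the infusion's starting clock time, in hours, with δ between −24 and 24. A draw on day d is then at 24(d − s) + δ hours.

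- Arm B Day 5 is at 96 + δ. It drops below 96 h when δ is negative, but cannot drop below 72 h.
- Arm B Day 3 and Arm A Day 5 are both at 48 + δ. The same negative δ takes both below 48 h.
- Example: a noon start and a 06:00 draw give δ = −6. Arm B Day 5 is at 90 h, and Arm B Day 3 and Arm A Day 5 are both at 42 h.

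Clock time can therefore bring Arm B's Day 5 draw inside 48–96 h, at the cost of moving Arm A's Day 5 draw out of window. It never brings Arm B's Day 5 draw inside 48–72 h, and it never turns Arm B's Day 3 draw into a pre-infusion sample.

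**Step 4: the windows against each other.** Read in hours, 72 ± 24 is 48 to 96, so Section 9.1 agrees with 9.3.3.1. Footnote g stops 24 h earlier, at 72 h.

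**Step 5: number affected.** Section 13.2 plans 20 of 60 patients in Arm B, which is one third. That is the upper bound. If footnote g's blast limit applies, the number is smaller and cannot be derived from the documents.

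**The case against.** The strongest reply is that the text already has the right anchor. Every mark carries footnote g, and footnote g, 9.3.3.1 and the 9.1 table all time samples 2 and 3 from the infusion. A site that reads the footnote would draw Arm B on Day 1 and Day 3. This stands as far as it goes: the harm is possible, not certain. But the marks and their footnote still disagree, and sites may resolve the disagreement differently.

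A reader might infer that Arm B loses its before-and-during pair altogether. The documents do not support that. The Pre-Rand sample precedes all study drug, and the Day 3 draw is nominally at 48–72 h, inside every stated window. Arm B also has no veliparib lead-in, so its screening and Day 1 samples would both be drug-free, and missing the second costs less than it would in Arm A. Screening is still not a full substitute: the protocol asks for both draws, and Section 10 lets baseline work precede therapy by up to a week.

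A reader might also infer that Arm B would show little induction and that the difference would be credited to veliparib. That goes too far. The plan does not define 4c as the change from sample 2 to sample 3, and it specifies no between-arm comparison of this assay.

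Finally, the extracted table is misaligned elsewhere; for example, the Day 14 marrow mark falls under the Day 8–13 heading. The calibration here uses the drug rows and not the headings, so the Day 3/Day 5 reading does not depend on them.

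**Conclusion.** The point holds as an internal contradiction. The calendar row agrees with footnote g and 9.3.3.1 for Arm A and not for Arm B. Followed literally, Arm B has no draw just before the infusion, its second draw is mid-infusion, and its third is outside footnote g's window and, except at or near 96 h, outside that of 9.3.3.1. Usable samples remain, but under the wrong numbers, so a comparison by sample number or calendar day would mix timing with arm.

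It concerns at most 20 patients. To say that all 20 are affected would ignore footnote g's blast limit. The assay serves a secondary objective but is classed as exploratory in Section 9.1, and the primary endpoint, sample size and power are unaffected. The conclusion rests on the column reading in Step 1 and on the Section 5.1 convention that the infusion begins at the start of its first day. It is worth correcting because a small edit removes it.

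**What to change.** - Split the row by arm: Arm A on Day 3 before the infusion and on Day 5; Arm B on Day 1 before the infusion and on Day 3. Alternatively, replace the day marks with hours from infusion start. Both follow the protocol's own text.
- Record the actual hours from infusion start for each sample, and analyze by those hours, not by sample number or calendar day.
- Settle one window for sample 3 across Section 9.1, Section 9.3.3.1 and footnote g.
- State in both 9.3.3.1 and footnote g whether the limit on circulating blasts applies.

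The cost is one calendar row, its footnote and matching lines in Section 9. The number of tubes does not change, and the calendar already has blood drawn on Day 1 for the blood count and chemistry.

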## 11. MEASUREMENT OF EFFECT

### 11.1 Antitumor Effect – Hematologic Tumors

#### 11.1.1 Duration of Response

Duration of overall response: The duration of overall response is measured from the time measurement criteria are met for CR or PR (whichever is first recorded) until the first date that recurrent or progressive disease is objectively documented (taking as reference for progressive disease the smallest measurements recorded since the treatment started).

The duration of overall CR is measured from the time measurement criteria are first met for CR until the first date that progressive disease is objectively documented.

Duration of stable disease: Stable disease is measured from the start of the treatment until the criteria for progression are met, taking as reference the smallest measurements recorded since the treatment started, including the baseline measurements.

#### 11.1.2 Progression-Free Survival

PFS is defined as the duration of time of randomization to time of progression or death, whichever occurs first.

#### 11.1.3 Response Review

Response will be graded by the principle investigator, and will be according to the response criteria below.

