### Aggressive Myeloproliferative Disorders

Complete remission (CR): The patient must be free of all symptoms or signs related to MPD and have a white blood cell count (WBC) between 1 and  $10 \times 10^9/L$  with no peripheral blood blasts, promyelocytes or myelocytes and normalization of bone marrow (<5% blasts in normocellular or hypercellular marrow) for at least 4 weeks; resolution of pretreatment cytopenias including Hgb  $\geq 12.0 \text{ gm/dl}$  ( $\geq 11.0 \text{ gm/dl}$  for females) without erythropoietin or transfusion support; ANC  $\geq 1.0 \times 10^9/L$  and platelet count  $>100 \times 10^9/L$  without support; and resolution of pretreatment hyperleukocytosis and/or thrombocytosis ( $>450 \times 10^9/L$ ).

Partial remission (PR): improvement in two or more of the following: 1) ANC increase of 100% up to  $>10^9/L$  for neutropenia and WBC count between 1 and  $10 \times 10^9/L$  with persistence of immature cells (blasts, progranulocytes, myelocytes); 2) increase in Hgb of 2 gm/dl if baseline value was  $<10 \text{ gm/dl}$  and a decrease in transfusion requirements by at least 50% (frequency and/or volume); 3) persistent thrombocytosis  $>450 \times 10^9/L$  but  $<50\%$  of pretreatment values; 4) reduction in bone marrow blasts to  $\leq 5\%$  if blasts were  $>10\%$  in normocellular or hypercellular marrow; and 5) reduction in splenomegaly and/or hepatomegaly by 50% of pretreatment dimensions.

These definitions are consistent with those published by Giles et al. (48).

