### Acute myeloid leukemia

The following definitions are consistent with those published by Cheson/Dohner et al for acute leukemia (47).

**Complete Remission (CR):** Bone marrow showing less than 5% leukemic blasts with normal maturation of all cell lines, an ANC of at least 1000/ $\mu$ L and a platelet count of 100,000/ $\mu$ L, absence of blast in peripheral blood, absence of identifiable leukemic cells in the bone marrow, clearance of disease-associated cytogenetic abnormalities, and clearance of any previously existing extramedullary disease. Repeat marrow confirmation 4-6 weeks following the marrow documenting CR is not required due to the need for continued treatment in CR.

**Complete Remission with Incomplete Recovery (CRI):** All CR criteria except for residual neutropenia (ANC < 1000/ $\mu$ L) or thrombocytopenia (platelets < 100,000/ $\mu$ L).

**Partial remission (PR):** The presence of trilineage hematopoiesis in the bone marrow with recovery of ANC and platelets to the above stated levels, but with 5 to 25% bone marrow blasts, AND at least 50% decrease in bone marrow blast percentage from baseline.

**Clinical improvement/Minor Response (MR):** Non-progressive disease with at least a 20% decrease in marrow blasts and/or a decrease in leukemia-related symptoms (e.g., fever, bone pain, splenic pain, transfusion requirements) and signs (decrease in extramedullary site of leukemia).

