### **12.1 Study Oversight**

This protocol is monitored at several levels, as described in this section. The Protocol Principal Investigator is responsible for monitoring the conduct and progress of the clinical trial, including the ongoing review of accrual, patient-specific clinical and laboratory data, and routine and serious adverse events; reporting of expedited adverse events; and accumulation of reported adverse events from other trials testing the same drug(s). The Protocol Principal Investigator and statistician have access to the data at all times through the CTMS web-based reporting portal.

All Study Investigators at participating sites who register/enroll patients on a given protocol are responsible for timely submission of data via Medidata Rave and timely reporting of adverse events for that particular study. This includes timely review of data collected on the electronic CRFs submitted via Medidata Rave.

All studies are also reviewed in accordance with the enrolling institution's data safety monitoring plan.

In addition, the Protocol Principal Investigator will have at least monthly conference calls with the site Study Investigators and study teams to review accrual, progress, adverse events, and unanticipated problems.

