## 13. STATISTICAL CONSIDERATIONS

### 13.1 Study Design/Endpoints

This phase II study will randomize patients 2:1 to Arm A (T/C/V) or to the standard Arm B (T/C), respectively. The primary end point is Overall Response (CR/CRi). We expect that these MPN patients will fall into two risk categories based on the percent blasts at baseline: < 20% blasts versus 20% or higher. The expected CR/CRi rate with traditional regimens in this group of patients ranges from 14% for patients with worse disease to 29% for patients with blasts 20% or higher.

For each group, the level of response that would confer interest in pursuing the therapy is a CR/CRi rate of 58%. This CR/CRi response rate was the response rate seen in our phase I trial in the subset of MPN patients with a lower response rate (those with less than 20% blasts), where we observed responses in 7 out of 12 cases (58.3%). The proportion of patients in each subgroup are assumed to be 33% in the low blast count group and 67% in the higher blast count group, respectively. These proportions are considered in the sample size calculation. The final analysis will be by an exact Cochrane-Mantel-Haenszel test, which tests for an overall treatment difference while adjusting for subgroup. The primary analysis will conclude a significant benefit for Arm A over Arm B if the one-sided p value < 0.10.

The study design includes interim monitoring for futility (i.e., stopping early if there is high probability that the study will not show a significant benefit for Arm A over Arm B). Futility is based on the predictive probability of a statistically significant treatment difference at the end of the study if the study enters, treats, and follows the total number of patients planned for the study. If we determine at any interim analysis that there is a < 10% chance of ultimately finding a statistically significant difference between Arm A and Arm B, we will pause for a safety review by the PI, study team, and CTEP if one of the stopping boundaries is hit. We determined the predictive probability of a significant trial result through simulations using a beta-binomial model to predict future observations conditional on data available at the time of the test. In the simulations, the predicted test was an exact Cochran-Mantel-Haenszel test, and a predicted test was significant if the one-sided p value of the test was < 0.10, as stated in the primary analysis.

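### CR/CRi is graded by an investigator who evidently knows the arm, under overlapping criteria sets that can turn identical AML data into response or non-response

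*Combined protocol and SAP*

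**What the plan says.** Section 11.1.3 (Response Review): "Response will be graded by the principle investigator, and will be according to the response criteria below". Four sets of definitions follow, for aggressive MPD, MPD transformed to acute leukemia, CMML and AML. Some items are numerical and others need judgement. Under aggressive MPD, for example, "The patient must be free of all symptoms or signs related to MPD". CRi appears only under the AML heading, as "All CR criteria except for residual neutropenia" or thrombocytopenia. The response categories in Section 13.7.2 include complete and partial response but not CRi.

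Section 13.1 makes CR/CRi the primary endpoint. On the test: "The final analysis will be by an exact Cochrane-Mantel-Haenszel test, which tests for an overall treatment difference while adjusting for subgroup". On the decision rule: "The primary analysis will conclude a significant benefit for Arm A over Arm B if the one-sided p value < 0.10". The futility looks in Sections 13.1 and 13.2 project that same test.

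Section 5.1 gives Arm A oral veliparib on days 1-21 with the infusion on days 3-7. Arm B has the infusion on days 1-5, and no placebo is described. Section 12.1: "The Protocol Principal Investigator and statistician have access to the data at all times".

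**The concern.** A binary endpoint graded with the arm in view can drift in favour of one arm. That risk is larger here because the grader may also have a choice of rule. Section 3.1.1 admits AML, new or relapsed, only when it follows an antecedent myeloproliferative disorder. Each such patient therefore fits two headings in Section 11.1.3: transformed MPD and AML. The plan does not say which governs, or that the choice is made before treatment.

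CR/CRi is the only input to the primary test and to the futility projections. A few borderline patients read differently by arm would move the trial's conclusion directly.

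**Working it through.** **Step 1. The two sets for AML after MPD, side by side (Section 11.1.3)**

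| Item | MPD transformed: CR | AML: CR or CRi |
|---|---|---|
| Marrow blasts | <5% | <5%, with normal maturation |
| ANC and platelets | above 1 and above 100 × 10⁹/L | same levels for CR; either may be low for CRi |
| CRi category | none | defined |
| Spleen | clearance required by name | extramedullary clearance; spleen not named |
| Leukemia symptoms | must be absent | not listed |
| Cytogenetics | not listed | clearance required |

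Patient 1 has under 5% blasts and platelets below 100 × 10⁹/L, and meets every other item in both columns. The AML set gives CRi, a responder. The transformed set gives neither CR nor CRi, a non-responder.

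Patient 2 has recovered counts and under 5% blasts, and meets every other item, but a disease-associated karyotype persists. The transformed set gives CR. The AML set gives neither CR nor CRi.

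Neither set is always the stricter, so a choice made patient by patient can go either way. CMML with at least 20% marrow blasts, which Section 3.1.1 calls transformation, could arguably fall under the CMML set as well. The overlap lies mainly in the ≥20% blast stratum, assumed in Section 13.1 to be 67% of patients.

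**Step 2. Reproducing the design**

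Inputs from Sections 13.1 and 13.2:
- 40 patients in Arm A and 20 in Arm B, with 33% / 67% in the low- and high-blast strata, taken as 13A/7B and 27A/13B
- one-sided 0.10
- looks at 16/8 and 28/14
- stop if predictive probability is below 0.10 under a beta(1,1) prior
- null rates 0.29 (<20% blasts) and 0.14 (≥20% blasts), from the Section 13.2 table

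Test: given the responder total in each stratum, Arm A's count in that stratum is hypergeometric. The two distributions are convolved, and the p-value is the probability of an Arm A total at least as large as observed. Rejection probability is the sum, over all binomial outcomes that pass both looks, of outcome probability × 1[p < 0.10].

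| Quantity | Section 13.2 | Enumerated |
|---|---|---|
| Power at 0.58 | 0.91 | 0.908 |
| Rejection at 0.40 | 0.475 | 0.496 |
| Rejection under null | 0.036 | 0.043 |
| Early stopping under null | 0.852 | 0.825 |

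The plan's figures come from 1,000 simulations, with standard errors √(p(1−p)/1000) of 0.009, 0.016, 0.006 and 0.011. The first three rows agree within about 1.3 standard errors. The fourth is (0.852 − 0.825)/0.011 ≈ 2.5 standard errors lower, so the enumerated rule stops slightly less often than the plan's simulation. Power reproduces.

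**Step 3. Differential grading, as an assumption**

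Arm B is read correctly. Arm A is read d points high in both strata, so its observed rates are 0.29 + d and 0.14 + d. Expected true Arm A responders are 13 × 0.29 + 27 × 0.14 = 7.55. Five points adds 40 × 0.05 = 2 patients, and ten points adds 4.

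| Arm A optimism (points) | Null rejection, with futility stopping |
|---|---|
| 0 | 0.043 |
| +2 | 0.063 |
| +4 | 0.088 |
| +5 | 0.103 |
| +10 | 0.199 |

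- Without futility stopping, going from 0 to +5 points takes the rate from 0.049 to 0.116.
- If 5% of true Arm A non-responders are upgraded instead: 0.088.
- If both arms are read 5 points high: 0.047.
- Section 13.1's text ties the 29% control rate to the ≥20% blast group, while the Section 13.2 table ties it to the <20% group. With the rates swapped, +5 points takes the rate from 0.046 to 0.103.

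**The case against.** Most of the endpoint rests on laboratory thresholds and marrow counts, which leave limited room for optimism. The documents report no grading bias, and the 5 points are the reviewer's assumption. Section 11.2 already plans a second report under published MPN blast-phase criteria, and under MDS/MPN criteria for CMML. Section 12.2 provides continuous data review and audits three times a year. A futility boundary leads to a pause for review, not an automatic stop. Section 11.1.3 may also mean site investigators, in which case no single person grades the trial.

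Much of this stands. The second report and the audits would help to show selective grading, but they neither mask the grader nor say which set governs the primary result. If sites grade, the treating team still sees the regimen. The overlap in Step 1 does not depend on any assumed bias.

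Four stronger readings are tempting, and the documents do not support them:
- A reader might infer that the protocol declares the grader unmasked. It does not; this is an inference from the regimens and from data access.
- A reader might infer that error control is lost because 0.043 more than doubles to 0.103. The starting point is the conservative actual size of the exact test with futility stopping, and +5 points only brings it to about the nominal 0.10.
- A reader might infer that CR/CRi could be derived wholly by program from counts and blasts. Symptoms, spleen or extramedullary disease, dysplasia and cytogenetics need recorded judgements, and CRi has no rule outside AML.
- A reader might infer that grading from a listing without the arm would mask the investigator. It would not mask someone who has continuous data access.

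**Conclusion.** The concern holds in this form. The primary endpoint is graded by an investigator who evidently knows the arm. For AML after MPD, two criteria sets can give opposite primary outcomes from identical data, and the set can be chosen after outcome and arm are known.

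The size of any resulting bias is unknown. Under the stated null rates, the nominal one-sided 0.10 is reached at roughly 5 points of optimism confined to Arm A, about two patients in 40, and the rate is about twice nominal at 10 points. Below 5 points, rejection stays under 0.10 with futility stopping. Optimism shared by both arms hardly matters. These figures assume fixed stratum sizes; averaging over random stratum splits gives 0.043 to 0.102 at +5 points.

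**What to change.** 1. State in Section 11.1.3 which criteria set governs each disease group, including CMML with at least 20% blasts, and whether CRi counts in each. Reconcile the transformed-MPD, CMML and AML definitions with the categories in Section 13.7.2.
2. Record each patient's governing set at randomisation, alongside the blast stratum already captured there (Section 13.3).
3. Check the numerical components of the full protocol definition by program: marrow and peripheral blasts, ANC and platelets, plus WBC, hemoglobin, transfusion status and duration where the set requires them.
4. Record the judgement items as separate fields: symptoms, spleen or extramedullary disease, dysplasia and cytogenetics.
5. List disagreements between the programmed result and the investigator's grade, and run the primary test on the programmed result as a sensitivity analysis.
6. Say in Section 11.1.3 whether the site or the protocol principal investigator grades.

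The cost is a protocol clarification, the added CRF fields and some programming. No patient procedure or extra assessor is needed. Items 1 and 2 close the choice of set. Items 3 to 5 make differential grading visible, but do not remove it from the judgement items.
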